(<https://www.cancer.gov/publications/patient-education/clearing-the-air>) that provided education and guidelines for quitting and a Quitline telephone number (SIM participants also received the booklet). This reflected “treatment as usual” for tobacco cessation in the context of outpatient treatment for CUD. SEQ participants interested in tobacco cessation during Phase 1 could make cessation attempts but had to obtain tobacco medications on their own. During Weeks 13-24, (Phase 2), SEQ participants were offered the TI as described above, and encouraged to attend weekly clinic visits to help facilitate engagement and adherence. Note that during Phase 2 clinic staff were highly flexible and encouraging of any attendance schedule with the primary goal of accommodating participants so that they could complete TI modules and obtain NRT.

2.3.3 Primary Hypotheses. Based on prior pilot study and the literature on targeting tobacco use in the context of treatment for other SUDs, we hypothesized that: (1) the TI would be acceptable to participants in the SIM condition (i.e., Phase 1 retention and CUD engagement would not differ between conditions, and that the majority of SIM participants would engage with the TI components; (2) during Phase 1, the SIM condition would engender greater use of NRT, more tobacco quit attempts, greater sustained tobacco abstinence than SEQ, and cannabis abstinence would not differ between conditions; (3) at the end of Phase 2, after participants in both conditions were exposed to the TI, a greater percentage of SIM than SEQ participants would have initiated NRT and made a tobacco quit attempt.

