2.4 Measures

2.4.1 Substance Use. At intake, the Substance Use Disorders section of the SCID (First et al., 1995) was administered to determine SUD diagnoses. The timeline follow-back (TLFB) procedure (Sobell and Sobell, 1992) was used to obtain self-reported substance use information for the 90 days preceding intake, and then again at each clinic visit to assess substance use since the last clinic visit. TLFB assessments included cannabis, cigarettes, other tobacco and nicotine products (including smokeless tobacco and electronic cigarettes), alcohol, other drug use, and NRT use. Nicotine dependence was assessed at baseline using the Fagerstrom Test of Nicotine Dependence (FTND; Heatherton et al., 1991).

Cannabis abstinence was verified via twice-weekly observed collection of urine specimens which were then tested immediately thereafter. Cannabis and adulterant testing were performed using dipstick tests with a minimum THC detection cutoff of 50 ng/ml (<http://www.americanscreeningcorp.com>). Failure to submit a specimen without an excused absence was treated as a cannabis-positive result.

Self-reported tobacco abstinence was verified using expired carbon monoxide (CO; coVita Micro + Smokerlyzer: <http://covita.net/micro+.html>). Participants with a CO level ≤ 5 were considered tobacco abstinent. In the event of self-reported tobacco abstinence, a breath CO > 5 , and self-reported cannabis use (which could increase CO level), tobacco abstinence was verified using urine cotinine (ONSCREEN Cotinine Test; <http://www.americanscreeningcorp.com>).

2.5 Outcomes. Primary engagement outcomes included Phase 1 treatment retention defined as clinic attendance, and treatment engagement defined by completion of cannabis and tobacco computer modules, and initiation and duration of NRT. The primary cannabis outcome was the duration of continuous abstinence achieved during Phase 1, assessed using the twice-weekly observed urine specimens. Primary tobacco outcomes included the percent of participants who

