made at least one self-reported tobacco quit attempt during Phase 1, and percent of participants who achieved sustained tobacco abstinence over the final eight weeks of Phase 1. Secondary outcomes included: percent of participants who achieved any biologically-verified cannabis or tobacco abstinence (≥ 1 negative urine THC/cotinine specimen or expired carbon monoxide < 5 ppm), percent of participants who achieved cannabis abstinence throughout the final four weeks of treatment, reduction in percent days of cannabis and tobacco use during treatment relative to baseline, and point-prevalence cannabis and tobacco abstinence at the 12-week follow-up assessment.

2.6 Data Analysis. Sociodemographic and baseline drug use characteristics between treatment conditions were compared using t-tests for continuous measures and chi-square tests for nominal measures (Table 1). The primary cannabis and tobacco abstinence outcomes were analyzed using an intent-to-treat approach with missing biological verification data and dropouts treated as a positive indicator of cannabis or tobacco use. Longest duration of continuous abstinence from cannabis (primary), number of days abstinent from tobacco, and number of tobacco quit attempts (primary) were all zero-inflated and therefore could not be analyzed with models that assume continuous, normally distributed outcomes. We therefore analyzed each of these outcomes using a zero-inflated Poisson model which provides an odds ratio describing the relative likelihood of achieving a zero-response to the outcome in the two treatment arms and a ratio of means describing the relative mean of the outcome in the two treatment groups. Additionally, several binary outcomes were analyzed via chi-square tests: cannabis abstinence in the final 4 weeks, point prevalence abstinence at the end of treatment, achievement of at least 50% reduction in days of using cannabis from intake to the final 4 weeks, and achievement of continuous tobacco abstinence for ≥ 2 consecutive weeks. Phase 2 outcomes were analyzed using descriptive statistics. Statistical comparisons were not made between SEQ Phase 2 and SIM Phase 1 outcomes because of the lack of Phase 2 data due to only a 30% participation rate for SEQ during Phase 2. All analyses were performed using SAS version 9.4.

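### The zero-inflated Poisson analysis in 2.6 gives count-part p-values that depend on an unstated unit and unreported dispersion, misdescribes its ratio as the ratio of arm means, and disagrees with 2.5 on the form of the quit-attempt primary

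*Combined protocol and SAP*

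**What the plan says.** Section 2.5 defines the cannabis primary: "The primary cannabis outcome was the duration of continuous abstinence achieved during Phase 1, assessed using the twice-weekly observed urine specimens". Section 2.6 takes the longest such run, groups it with tobacco-abstinent days and the number of quit attempts, and gives excess zeros and non-normality as the reason for its model: "We therefore analyzed each of these outcomes using a zero-inflated Poisson model which provides an odds ratio". It describes the second estimate as "a ratio of means describing the relative mean of the outcome in the two treatment groups". The tobacco outcome beside it is in days, but no unit is given for the cannabis run. No dispersion check, robust variance or negative binomial alternative is mentioned.

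For quit attempts, 2.5 lists as primary the percentage of participants who "made at least one self-reported tobacco quit attempt during Phase 1". Section 2.6 attaches the primary label to the count: "number of tobacco quit attempts (primary) were all zero-inflated". In 2.3.3, hypothesis 2 (Phase 1) expects "more tobacco quit attempts" under SIM and that "cannabis abstinence would not differ between conditions". Hypothesis 3, for the end of Phase 2, expects that "a greater percentage of SIM than SEQ participants would have initiated NRT and made a tobacco quit attempt".

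**The concern.** Zero inflation answers one objection to a plain Poisson model, the surplus of zeros. It leaves the other untouched: among participants not certain to be zero, the variance is still forced to equal the mean. A longest run of abstinence is a duration, not a count of independent events, and nothing makes its variance match its mean in any unit. If it does not match, the count-part standard error is wrong, and how wrong depends on the unit chosen.

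The second issue is interpretation. A reader who takes the ratio as the comparison of arm means, as 2.6 invites, may read a value near 1 as agreement with the no-difference hypothesis when the arm means differ.

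The third is that a primary outcome has two forms. A percentage and a mean count are different estimands with different tests, and the documents do not say which one decides.

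**Working it through.** **Inputs.** 67 participants enrolled (2.1). Phase 1 lasts 12 weeks with specimens twice weekly (2.2.1), so a run is 0–24 specimens, and one specimen is half a week or 3.5 days. The text gives no arm sizes, zero fractions, run distribution or significance level. Assumed: arms of 34 and 33, two-sided 0.05, and the distributions named below. The documents state no design figure to reproduce.

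**Unit and dispersion, closed form.** Write φ for variance/mean in the non-zero class. The ZIP standard error of log λ assumes φ = 1; the true one is larger by about √φ. For large λ, the rejection rate under the null is about 2 × [1 − Φ(1.96/√φ)]. Changing the unit by a factor c multiplies the variance by c² and the mean by c, so φ becomes cφ. If φ = 1 in specimens:

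- weeks, φ = 0.5: 1.96/0.707 = 2.77, giving 0.6%
- specimens, φ = 1: 5%
- days, φ = 3.5: 1.96/1.871 = 1.05, giving 29%

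At most one unit can be correctly calibrated.

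**Unit and dispersion, simulation.** Null rejection by the model-based count-part Wald test (3,000 replicates for the first two rows, 4,000 for the rest; 30% and 50% zeros, then 40% and 60%). The same kind of runs is recorded in three units:

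| Assumed non-zero runs | Weeks | Specimens | Days |
|---|---|---|---|
| Exactly ZIP in specimens, λ = 8 | 0.5–0.7% | 5.2–5.5% | 29–30% |
| Uniform on 1–24 | 15–16% | 32–33% | 59–60% |
| 1 + beta-binomial(23; 5, 10) | 1.8–2.2% | 9.6–10.5% | 38–39% |
| 1 + beta-binomial(23; 1, 2) | 15–16% | 32–33% | 58–60% |
| 1 + beta-binomial(23; 0.7, 1.0) | 20% | 37–38% | 63–64% |

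Sandwich errors gave 4.7–6.5% in the last three rows, about 5–6% in a repeat of the first two at 40% zeros, and no more than 7.2% in any set run. More extreme shapes widen the model-based range to 0–72%. When the data are exactly ZIP in the unit fitted, the test holds its size (4.6–5.3%).

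In one simulated data set the ratio barely moved across weeks, specimens and days (0.88, 0.91, 0.91). Its model-based standard error fell from 0.151 to 0.108 to 0.058, and p went from 0.41 to 0.36 to 0.095. The robust standard error stayed at 0.145–0.148.

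The other two outcomes behave similarly. For tobacco days (0–84), model-based rejection was 51–61% for widely varying values and 4.9% for exact ZIP, against 5.5–8.5% with sandwich errors. For quit attempts it was 10–19% if overdispersed and 4.9% if exact ZIP, against 6.8–8.6%.

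**Ratio.** In a standard ZIP the arm mean is (1 − π)λ, so

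arm-mean ratio = (λ₁/λ₀) × (1 − π₁)/(1 − π₀).

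With equal λ and π = 0.6 versus 0.3, the ZIP ratio is 1.00 but the arm-mean ratio is 0.4/0.7 = 0.57. With λ = 6 versus 4 and π = 0.6 versus 0.4, the ZIP ratio is 1.50 but the arm means are equal: 0.4 × 6 = 0.6 × 4 = 2.4. The two ratios agree only when the structural-zero shares agree.

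**Quit attempts.** The probability of no attempt is π + (1 − π)e^(−λ), whereas the zero-part odds ratio compares π alone.

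- With π = 0.3 in both arms and λ = 2 versus 1, the zero-part odds ratio is 1.00, yet the percentages with an attempt are 1 − (0.3 + 0.7 × 0.135) = 60.5% and 1 − (0.3 + 0.7 × 0.368) = 44.2%.
- With π = 0.3 versus 0.5, the zero-part odds ratio is 0.43, while the odds ratio for no attempt is 0.61, 0.53 or 0.46 at a common λ of 0.8, 1.5 or 3.

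So the ZIP zero part is not the percentage defined in 2.5.

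**The case against.** The strongest reply is that harm is not shown. Every error rate above rests on assumed distributions, and the documents report no p-value. Section 2.6 is a short account in the past tense, and silence about a dispersion check is not evidence that none was made. All of this stands. A reader might infer that the cannabis test was too liberal, or that a unit was picked to suit the result; the documents support neither. Nor does inflation help the authors here: hypothesis 2 expects no cannabis difference, so a liberal test would tend to produce a false difference, and only a conservative one would give false support.

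One could also say that 2.5 implies specimens as the unit. It points that way, but even in specimens the simulated rejection ran from about 5% to 38%, so dispersion still matters.

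On the ratio, 2.6 presents it beside the zero-part odds ratio, and reading the two together is correct practice. With π = 0.6 versus 0.3 (odds ratio 3.50), the zero part is significant in 70% of simulated trials; with 0.6 versus 0.4 (arm-mean ratio 0.67), in 38%. The joint reading helps but does not make the description right. A marginalized ZIP would fit the wording, but none is mentioned.

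On quit attempts, the Phase 1 hypothesis suits a count, so the count is not an unreasonable choice. The percentage is missing from the chi-square list, but that is weak evidence: the list is not presented as complete, and the other tobacco primary, sustained abstinence over the last eight weeks, is missing too. A reader might infer a switch of outcome after the results were seen, or that the two forms would give opposite answers. The documents show no dates for either choice and no data, so neither follows. What stands is the conflict between 2.5 and the label in 2.6.

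**Conclusion.** The concern holds in limited form, and the plan should be corrected. Two faults are visible on the page: the ratio is described as something a standard ZIP does not estimate, and a primary outcome takes different forms in 2.5 and 2.6. The third is a method weakness: with model-based errors, the count-part p-value for the cannabis primary depends on a unit and a dispersion that are not given. The plausible size is about 1% to 60% rejection at nominal 5%, against about 5–6% with sandwich errors, under the assumed arm sizes, zero fractions and run shapes. These figures show how far the test can stray, not how far it did. The trial's own error could be in either direction or negligible. The dispersion and unit fault does not extend to the zero-part odds ratio for the cannabis run.

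**What to change.** 1. Keep the two-part model, but use sandwich standard errors for the count part, or a negative binomial or hurdle form, for all three outcomes. Report dispersion. State the unit actually analysed for the cannabis run, and how excused absences enter it: 2.4.1 exempts them from being scored positive without saying what they do to a run, while 2.6 scores missing verification data as positive.
2. Describe the ratio as the ratio of means in the not-always-zero class, to be read with the zero-part odds ratio. Add the arm-mean ratio or difference with a bootstrap confidence interval, labelled post hoc because 2.6 was written with results in hand.
3. Reconcile 2.5 and 2.6 on quit attempts. Report both the percentage (chi-square test, with a confidence interval for the difference) and the count. Say which form was specified before results were known, and label the analysis post hoc if that cannot be shown.

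The cost is a few sentences and a short reanalysis of data already collected. There are downsides. Intervals will usually widen if runs are overdispersed. Sandwich errors remain slightly liberal at this sample size (about 5–9% across the three outcomes). A test of means can have less power than the zero part when arms differ mainly in zeros: using a t-test, 60% against 71% for zeros of 0.6 versus 0.3 with λ = 8, and 49% against 72% with uniform runs. It should therefore supplement the zero part, not replace it.

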Official Title:	Clinical Trial Tobacco Marijuana
NCT number:	02277665
Document Type:	Cover Letter and Protocol
Date of the Document:	August 1, 2018

Study Protocol and Analysis Plan

2.1 Participants. Participants seeking treatment for CUD were enrolled between October 2014 to September 2016 at Dartmouth College and the University of Washington. The study was conducted in compliance with Internal Review Boards at Dartmouth College and the University of Washington and registered on clinicaltrials.gov (NCT02277665). Participants at both sites were recruited from advertisements posted online (Craigslist, Facebook), in newspapers, on radio, posters throughout the community, and notices to professionals and service agencies. Participants were included if they met the following criteria: 1) ≥ 18 years of age, 2) current diagnosis of cannabis abuse or dependence made using the Structured Clinical Interview for DSM-IV (SCID: First et al., 1995), 3) cannabis use on ≥ 45 of the past 90 days, 4) regular use of tobacco (i.e. ≥ 5 days per week) or report primary administration of cannabis via blunts/spliffs, and 5) self-reported at least minimal interest in quitting tobacco in the next six months during the pre-intake screening (i.e. rating of ≥ 2 on a 5-point scale). Exclusion criteria included: 1) current dependence (DSM-IV criteria) in the last 6 months on alcohol or any drug other than tobacco and cannabis with the exception of opiate dependence maintained with agonist replacement therapy, 2) use of non-tobacco nicotine (i.e. nicotine replacement therapy, NRT), or exclusive use of smokeless tobacco products, 3) currently in treatment for substance dependence, 4) severe psychological distress (e.g. active suicidal ideation, debilitating panic disorder), 5) medical condition that required physician approval before using NRT (e.g. pregnancy or myocardial infarction), 6) legal status that would interfere with participation, 7) living with someone enrolled in the study, 8) not fluent in English, or 9) living ≥ 45 miles from the study site.

Of the 146 participants screened for the study, 53 did not meet inclusion / exclusion criteria, 15 were eligible but declined treatment, and 11 did not enroll for other reasons (e.g. lost contact after intake) (see Figure 1). Sixty-seven adults (45 male), age 18-60 years signed a study consent and were enrolled. Participant characteristics by treatment condition are presented in Table 1.

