2.3 Trial Design, Treatment Conditions, Hypotheses

This two group, 24-week study randomized participants seeking treatment for CUD to either a simultaneous (SIM) or a sequential (SEQ) treatment condition (Figure 1). Urn randomization procedures balanced the conditions on the following baseline characteristics: cannabis abstinence prior to treatment initiation, tobacco dependence severity (low vs. high, based on the Fagerstrom), blunt/spliff smoker or not, ethnicity (African American or not), and gender. Assessments occurred at week 12 (end of Phase 1) and week 24 (end of Phase 2).

2.3.1. SIM Condition. During weeks 1-12 (Phase 1), participants in the SIM condition received immediate access to the previously described CUD and tobacco interventions. The first five CUD MET/CBT modules were completed in a fixed order starting at the first visit. The TI modules and NRT were also available starting at the first visit, but for most participants, this did not occur until the second visit due to time constraints. TI modules could be completed in any order selected by participants, but as per above, NRT was not available until the NRT education module was completed. Both the CUD and TI modules viewed during clinic visits could then be accessed remotely with an ID and password. During weeks 13-24 (Phase 2) SIM participants could continue to access the cannabis and tobacco intervention modules ad libitum remotely but did not attend clinic visits or receive additional NRT. SIM participants that expressed an interest in continuing NRT after Phase 1 were provided with a one-week supply and instructed on how to purchase additional NRT on their own. For those not interested in continuing use, NRT dose was tapered during weeks 10-12 to reduce the probability of nicotine withdrawal symptoms from discontinuation.

2.3.2 SEQ Condition. During Phase 1, SEQ participants received only the CUD MET/CBT/CM intervention. They could not access the TI modules, NRT was not provided by the clinic, and no counseling for tobacco cessation was offered. During their first visit, they were given a booklet on tobacco cessation, *Clearing the Air*

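### The primary cannabis comparison names no covariate, although 90-day cannabis-use days were collected at intake and are not an urn factor; adjustment could help, by an amount the documents do not fix

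*Combined protocol and SAP*

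**What the plan says.** Section 2.5 defines the endpoint: "The primary cannabis outcome was the duration of continuous abstinence achieved during Phase 1", measured from twice-weekly observed urine specimens. Section 2.6 finds this outcome zero-inflated and states: "We therefore analyzed each of these outcomes using a zero-inflated Poisson model". The model is described by two outputs, an odds ratio for a zero response and "a ratio of means describing the relative mean of the outcome in the two treatment groups". No other model term is mentioned. The text is silent on covariates; it does not say that none was used.

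A baseline measure of cannabis use exists. Under section 2.4.1, the timeline follow-back (TLFB) was used to "obtain self-reported substance use information for the 90 days preceding intake", and cannabis is among the substances listed. Section 2.1 makes "cannabis use on ≥ 45 of the past 90 days" an entry criterion, so the count should be known for all 67 participants.

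On balance, section 2.3 says: "Urn randomization procedures balanced the conditions on the following baseline characteristics: cannabis abstinence prior to treatment initiation". The other urn factors are tobacco dependence severity, blunt/spliff smoking, ethnicity and gender. The number of use days is not listed. Section 2.6 adds: "Sociodemographic and baseline drug use characteristics between treatment conditions were compared using t-tests for continuous measures", with chi-square tests for nominal measures. No adjustment follows from those tests.

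**The concern.** Entry admits anyone from 45 to 90 use days in 90, so people who used on half of the days and people who used daily enter the same comparison. Frequency of use before treatment plausibly bears on how long abstinence is achieved. If it does, leaving it out adds avoidable noise, and a chance excess of daily users in one arm moves the estimate. Baseline tests can reveal such an excess but do not correct for it.

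The direction of the hypothesis raises the stakes. Section 2.3.3 predicts that cannabis abstinence in Phase 1 will not differ between the simultaneous (SIM) and sequential (SEQ) arms, and gives no margin. The noisier the comparison, the more easily a real deficit under simultaneous treatment is read as no difference.

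**Working it through.** **Inputs from the documents.** 67 participants enrolled (section 2.1; the flow checks: 146 − 53 − 15 − 11 = 67). Two arms. Zero-inflated Poisson model with no covariate named. Use days confined to 45–90 of 90.

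**Inputs assumed.** Arms of 33 and 34, because neither arm sizes nor an allocation ratio appear in the text. Two-sided alpha of 0.05. Correlation rho between use days and the outcome, varied because the documents give none. The plan states no power, effect size or standard deviation (SD), so there is no design figure to reproduce.

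**Step 1: chance imbalance.** The standard error of the difference in baseline means, in SD units, is √(1/33 + 1/34) = 0.244. The 95% limit is 1.96 × 0.244 = 0.48 SD. The chance of exceeding 0.25 SD in either direction is about 31%, and of exceeding 0.5 SD about 4%. These figures assume simple randomisation. An imbalance of 0.244 SD shifts an unadjusted contrast by rho × 0.244, that is 0.02 outcome SD at rho 0.1 and 0.12 at rho 0.5.

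**Step 2: linear approximation to the precision gain.** Adjustment multiplies the variance by 1 − rho². For an effect that has 80% power unadjusted, adjusted power is Φ((1.960 + 0.842)/√(1 − rho²) − 1.960).

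| rho | variance factor | cut in standard error | power, from 80% |
|---|---|---|---|
| 0.2 | 0.96 | 2.0% | 81.6% |
| 0.3 | 0.91 | 4.6% | 83.6% |
| 0.4 | 0.84 | 8.3% | 86.4% |
| 0.5 | 0.75 | 13.4% | 89.9% |

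**Step 3: the zero-inflated Poisson model itself.** Simulations used 67 participants, about 50% excess zeros, a mean of about 4 units when not zero, and a standardised covariate in both model parts. All of these are assumptions except the 67.

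- *Joint two-degree-of-freedom arm test* (400 runs per scenario). Power, unadjusted versus adjusted, was 61.5% and 60.5% at |rho| of about 0.2, 57.5% and 59.3% at about 0.35, and 55.3% and 62.3% at about 0.5.
- *Log odds ratio* (no arm effect). Its SD did not fall with adjustment: 0.521 to 0.540, 0.475 to 0.514 and 0.495 to 0.562 for weak, moderate and strong prognosis. The adjusted odds ratio is conditional on the covariate, so it is not the same quantity. Its dependence on baseline imbalance did fall, from slopes of 0.31, 0.60 and 0.97 per SD to between −0.02 and 0.10.
- *Log ratio of means.* Its SD fell clearly only with strong prognosis (0.200 to 0.166).
- *Difference in covariate-standardised arm means* (no arm effect). Two separate simulations gave cuts in its SD of 1% and 4% at |rho| of about 0.23, 10% and 11% at about 0.42, and 21% and 26% at about 0.60. The linear formula gives about 3%, 9% and 20%. In the first of these simulations, the slope on baseline imbalance went from −0.47, −1.14 and −1.94 units per SD to 0.09, 0.00 and −0.11.

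The benefit therefore appears in the standardised mean difference, not in the odds ratio, and it is material only from a correlation of roughly 0.4 upward.

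**The case against.** The strongest reply is that the deciding input is missing. No correlation is given, and there are reasons to expect a low one. The 45-day floor restricts the range of use days. In addition, missed specimens and dropouts count as positive, so the outcome partly reflects attendance. At |rho| of about 0.2 the gain is negligible. This stands, and the point has to be conditional.

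A reader might infer that adjustment would lift power from 80% to 90%. That figure needs rho 0.5 and a linear model. In the zero-inflated Poisson simulation the joint test gained about 7 points at that correlation and nothing at about 0.2. This also stands.

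A reader might also infer that the reported comparison is biased or that the arms were in fact unbalanced. The documents support neither. Table 1 is not shown in the text available here. Chance imbalance is part of the sampling error of a randomised comparison, so imbalance and lost precision are largely one issue seen from two sides. The urn factor for pre-treatment abstinence is related to use days and may hold imbalance below the Step 1 figures, although it need not separate a 45-day user from a 90-day user.

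Finally, the document is dated August 2018, enrolment ended in September 2016, and section 2.6 is written in the past tense. A covariate chosen now cannot be called pre-specified. That is correct and governs how the adjusted result should be labelled.

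What the reply does not remove is the gap itself. The model description omits an available baseline measure of the same behaviour, and including it costs almost nothing.

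**Conclusion.** The point holds in conditional form. As described, the primary cannabis comparison has no term for baseline use days, the measure should exist for every participant, and randomisation did not balance it directly. If use days predict abstinence, adjustment removes nearly all of the estimate's dependence on chance imbalance. It also reduces the standard error of the mean difference by 1–4% at |rho| of about 0.23, 10–11% at about 0.42, and 21–26% at about 0.60. These sizes rest on assumed arm sizes, an assumed outcome distribution and an unknown correlation; the entry floor and the urn factor may push the true benefit toward the low end.

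The documents do not show that precision was lost, that the arms differed in use days, or that no covariate was fitted. Nor would one covariate cure the larger weakness of hypothesis 2, the lack of a margin. A difference with a confidence interval would still tell the reader more about that hypothesis than a non-significant crude contrast.

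**What to change.** State in section 2.6 whether the zero-inflated Poisson model contained any covariates. Add percent cannabis-use days in the 90 days before intake, as one continuous term, to both the zero part and the count part of the model for longest continuous cannabis abstinence. Report the covariate-standardised arm means and their difference with a 95% interval, beside the unadjusted result. Label the adjusted analysis post hoc unless it was documented before the data were seen.

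The cost is one or two sentences and one variable in the SAS model, with no new data. The downsides are two extra parameters (one in each part) with 67 participants, and an odds ratio that becomes conditional on use days, which is why the standardised means should be reported.
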